4 STUDY OBJECTIVES

The objectives of this study are:

- 1. To assess the effect of atorvastatin on pancreatic beta-cell function as measured by C-peptide after a liquid mixed meal stimulation in patients with newly diagnosed type 1 diabetes mellitus
- 2. To assess the effect on metabolic control as measured by HbA1c and insulin requirements
- To assess the safety and tolerability of atorvastatin in the treatment of newly diagnosed type 1 diabetes patients as indicated by adverse events, changes in physical examination, ECG and vital signs and changes in laboratory parameters that are relevant to safety
- To assess the effect on risk factors of diabetic complications as indicated by changes in serum lipids and CRP in patients with newly diagnosed type 1 diabetes
- 5. To assess the effect on systemic immune abnormalities in patients with type 1 diabetes mellitus as measured by effects on beta-cell autoantibodies, blood cytokines and chemokines on protein and transcriptional level

5 OVERALL STUDY DESIGN AND PROCEDURES

5.1 Study Design

This study will be conducted as a randomized, double-blind, placebo-controlled, outpatient, parallel group study in adult patients with recent onset type 1 diabetes. Patients will be randomly assigned to treatment with either atorvastatin or placebo in a one-to-one manner. The treatment phase will be 18 months for each patient. Patients who are withdrawn from the study during the first nine months of the treatment phase will be replaced. A maximum of 160 patients will complete all study procedures. The number of subjects included may be adjusted following an interim analysis as specified in section 9.9)

Starting dose will be 40 mg per day of atorvastatin or a matching number of placebo tablets. After a run-in period of 4 weeks the daily dose will be increased to 80 mg per day or matching placebo. In case of side effects (e.g. myalgia) the dose will be reduced to 40 mg per day by the discretion of the investigator.

Efficacy on beta-cell preservation will be assessed by means of two-hour mixed-meal tolerance tests at baseline and after 12 months and 18 months of treatment. Safety data and data on metabolic control will be obtained at baseline and after 3, 6, 12 and 18 months of treatment.

Patients should continue insulin treatment throughout the study. A tight glycemic control should be aimed (Target HbA1c ≤ 6.5 %) from Visit 2 on.

5.2 **Study Flow Chart**

Visit	Screening	Visit 1 *	Visit 2	Visit 3	Visit 4	Visit 5	Early Discontinuation
Time	-28 to -2 days	0	3 months (±2 weeks)	6 months (± 10 days)	12 months (± 2 weeks)	18 months (± 2 weeks)	
Informed consent	х						
Inclusion/Exclusion Criteria	х						
Randomization		X					
Demographic Data	х						
Medical History and concomitant Illnesses	х						
2 h MMTT		X			х	х	
12 lead ECG	х					х	х
Vital signs	х	X	х	x	x	х	х
Body height ¹ , weight and BMI		х	х	х	х	х	х
Physical examination	х					х	x
Adverse Events		х	х	X	х	х	х
Concomitant Medication	х	х	х	х	х	х	х
Documentation of Insulin dose	Х	Х	х	х	х	х	х
Drug accountability		X	х	x	x	х	x
Hematology	х	х	х	х	х	х	х
Clinical Chemistry ¹	х	х	х	х	х	х	х
Serum Lipids	х	х	х	х	х	х	х
Coagulation	Х						
Urinalysis	х						
Transcriptional studies		х	х				
Cytokines/chemokines		Х	х		х	х	
Beta cell autoantibodies	х			х	х	х	
HCG ²	х	Х	х	х	х	х	х
Plasma CRP		х	х		х	х	
HbA1c	х	х		х	х	х	х
Fasting C-peptide		X³			X ³	X³	

Visit 1 only ²only female patients ³ sampled during mixed meal tolerance test

^{*} Telephone contact: Day 28/ -4 days before the dose increase of the study medication

5.3 Study Procedures

The patients will be selected on the basis of a screening examination. After inclusion, each patient will be required to attend the study site for five scheduled visits during the study. The patient will attend all visits in a fasted state, i.e. without food intake for at least 10 hours. Before the dose of the study medication will be increased (after 4 weeks run-in), the investigator will contact the patient by phone to make sure that no side effects occured. At visits 1, 4 and 5 the patient will be required to comply with restrictions of insulin therapy prior to the mixed meal tolerance test as outlined in Section 8.16. If a patient is acutely ill (like e.g. presence of a common cold by the scheduled time of a visit), this visit should be postponed within the time window for this visit.

The following procedures will be performed during the course of the study

5.3.1 Screening Visit

The screening visit will be performed 28 to 2 days prior to Visit 1. Informed consent must be obtained prior to any study related activity (see section 10.3)

The following procedures will be performed (lab tests already on hand and not older than 28 days at time of visit 1 will not be repeated):

Check of inclusion and exclusion criteria (see sections 6.3 and 6.4)

Demographic data (see section 8.1)

Medical history and concomitant illnesses (see section 8.2)

Concomitant medication including insulin dose (see section 8.3)

Vital signs (see section 8.5)

Physical examination (see section 8.6)

12-lead ECG (see section 8.7)

Safety laboratory including urinalysis and coagulation (see section 8.8)

Serum Lipids (see section 8.9)

HCG (in women only) (see section 8.10)

Beta-cell autoantibodies (see section 8.12)

5.3.2 Visit 1

Visit 1 should be performed 28 days to two days after screening visit. Visit 1 should not be scheduled later than 3 months and not earlier than two weeks after the start of the insulin treatment of the patient.

The following procedures will be performed:

Randomization (see section 7.5)

Questioning for Adverse events (see section 8.17)

Concomitant medication including insulin dose (see section 8.3)

Body weight, height and BMI (see section 8.4)

Vital signs (see section 8.5)

Safety laboratory (see section 8.8)

Serum Lipids (see section 8.9)

HCG (in women only) (see section 8.10)

HbA1c and fasting C-peptide (see section 8.11)

Plasma CRP (see section 8.13)

Serum cytokines and chemokines (see section 8.14)

Transcriptional analysis (in a subset of 50 patients) (see section 8.15)

Two-hour mixed-meal tolerance test (see section 8.16)

Dispensing of study medication (see section 7.3)

5.3.2.1: Telephone contact

A telephone contact will be performed 4 weeks after the start of the run-in period (Day 28/-4 days), before the dose of the study medication will be increased from 40 to 80 mgs daily.

The following questions will be asked:

- Adverse events in general ("Have you experienced any problems since your last visit/contact?")
- Muscle related adverse events in particular; the investigator should pose the following three questions:
- 1. Did you suffer of any muscle pain during the last four weeks?
- 2. Did any muscle ache occur during the last four weeks that cannot be explained by unusual strenuous physical activity?
- 3. Did you experience any weakness of muscles during the last four weeks?

5.3.3 Visit 2

Visit 2 should be performed 3 months (± 2 weeks) after Visit 1.

The following procedures will be performed:

Questioning for Adverse events (see section 8.17)

Concomitant medication including insulin dose (see section 8.3)

Body weight and BMI (see section 8.4)

Vital signs (see section 8.5)

Safety laboratory (see section 8.8)

Serum Lipids (see section 8.9)

HCG (in women only) (see section 8.10)

Plasma CRP (see section 8.13)

Serum cytokines and chemokines (see section 8.14)

Transcriptional analysis (in a subset of 50 patients) (see section 8.15)

Collection of used, unused and partly used study medication and dispensing of study medication (see section 7.3)

5.3.4 Visit 3

Visit 3 should be performed 6 months (± 10 days) after Visit 1.

The following procedures will be performed:

Questioning for Adverse events (see section 8.17)

Concomitant medication including insulin dose (see section 8.3)

Body weight and BMI (see section 8.4)

Vital signs (see section 8.5)

Safety laboratory (see section 8.8)

Serum Lipids (see section 8.9)

HCG (in women only) (see section 8.10)

Beta-cell autoantibodies (see section 8.12)

Collection of used, unused and partly used study medication and dispensing of study medication (see section 7.3)

HbA1c (see section 8.11)

5.3.5 Visit 4

Visit 4 should be performed 12 months (± 2 weeks) after Visit 1.

The following procedures will be performed:

Questioning for Adverse events (see section 8.17)

Concomitant medication including insulin dose (see section 8.3)

Body weight and BMI (see section 8.4)

Vital signs (see section 8.5)

Safety laboratory (see section 8.8)

Serum Lipids (see section 8.9)

HCG (in women only) (see section 8.10)

HbA1c and fasting C-peptide (see section 8.11)

Beta-cell autoantibodies (see section 8.12)

Plasma CRP (see section 8.13)

Serum cytokines and chemokines (see section 8.14)

Two-hour mixed-meal tolerance test (see section 8.16)

Collection of used, unused and partly used study medication and dispensing of study medication (see section 7.3)

5.3.6 Visit 5

Visit 5 should be performed 18 months (± 2 weeks) after Visit 1.

The following procedures will be performed:

Questioning for Adverse events (see section 8.17)

Concomitant medication including insulin dose (see section 8.3)

Body weight and BMI (see section 8.4)

Vital signs (see section 8.5)

DIATOR

Protocol Version 2.3 07/01/2004

Physical examination (see section 8.6)

12-lead ECG (see section 8.7)

Safety laboratory (see section 8.8)

Serum Lipids (see section 8.9)

HCG (in women only) (see section 8.10)

HbA1c and fasting C-peptide (see section 8.11)

Beta-cell autoantibodies (see section 8.12)

Plasma CRP (see section 8.13)

Serum cytokines and chemokines (see section 8.14)

Two-hour mixed-meal tolerance test (see section 8.16)

Collection of all used, unused and partly used study medication (see section 7.3)

5.3.7 Early Discontinuation Visit

If the patient is prematurely discontinued from further study participation he/she will be invited to attend an early discontinuation visit. If the reason for discontinuation was an adverse event that is still present by the time of the early discontinuation visit, the adverse event will be followed up until it is resolved or stabilized.

The following procedures will be performed:

Questioning for Adverse events (see section 8.17)

Concomitant medication including insulin dose (see section 8.3)

Body weight (see section 8.4)

Vital signs (see section 8.5)

Physical examination (see section 8.6)

12-lead ECG (see section 8.7)

Safety laboratory (see section 8.8)

HCG (in women only) (see section 8.10)

HbA1c (see section 8.11)

Collection of all used, unused and partly used study medication (see section 7.3)

6 SELECTION OF STUDY POPULATION

The selection of study population should follow the guidelines by the International Immunology of Diabetes Society (11).

6.1 Primary Diagnosis

Male or female patients with the diagnosis of type 1 diabetes mellitus based on the criteria of the American Diabetes Association (12) no more than 3 months from start of insulin therapy.

6.2 Number of Subjects

It is aimed that a maximum of 160 patients will complete all study procedures. Patients will be randomized one-to-one to the active treatment or the placebo group. The number of patients may be adjusted following the interim analysis (see section 9.9).

Patients must meet all of the inclusion criteria and not meet any of the exclusion criteria before the first administration of study drug to be eligible for the study.

6.3 Inclusion Criteria

- Insulin treated patients with a newly diagnosed type 1 diabetes mellitus as defined by the ADA criteria at least two weeks but not later than 3 months after start of insulin treatment
- 2. Age18 to 39 years, inclusive
- Male patient or female patient using adequate contraceptive methods (oral contraceptives, intrauterine device, sterilization or consistent use of barrier methods like diaphragm and/or condoms in combination with spermicides) throughout the study
- Tested positive for at least one of the three islet autoantibodies GAD65, IA2 or ICA

6.4 Exclusion Criteria

- 1. History of a malignancy
- 2. Presence of a clinically significant hepatic or renal disease, as indicated, but not limited to a serum creatinine elevated more than ten percent above the upper limit of normal, elevation of AST or ALT more than 3 times the upper limit of normal

3. Any other acute or chronic condition that may affect the patient's response to treatment or might be associated with an increased risk for the patient to participate, as judged by the investigator

- 4. Current use of anti-inflammatory or immunmodulatory drugs, antihypertensive, lipid-lowering, or antidiabetic drugs other than insulin
- 5. Pregnant or nursing women or women intending to become pregnant during the course of the study
- 6. Patients with any significant diseases or conditions, including psychiatric disorders and drug abuse, that in the opinion of the investigator, are likely to affect the patient's response to treatment or his/her ability to comply with study procedures
- 7. Known or suspected allergy to atorvastatin or any component of the trial product
- 8. Known myopathy, myalgia or myositis with a serum CPK above 3 times the upper limit of normal
- 9. A serum-CPK above 5 times the upper limit of normal
- 10. Patients who have received any investigational drug within 3 months prior to Visit 1
- 11. Patients who had a severe blood loss (≥ 400 ml, e.g. blood donation) within 2 months prior to Visit 1
- 12. Patients have any significant laboratory abnormality at time of screening, such hemoglobin < 11 mg/dL, or any other clinically significant abnormal laboratory test result, as judged by the investigator
- 13. A serum LDL-cholesterol above 150 mg/dL at time of screening
- 14. Unwillingness to comply with the study procedures, as judged by the investigator

6.5 Withdrawal Criteria

During the study, each subject may withdraw from further participation at any time and without giving reasons. However, adequate efforts should be made to determine the reasons for discontinuing. If a patient is lost to follow-up, adequate effort should be made to determine the whereabouts and medical status of that patient, and to recover the study medication.

Patients may be discontinued early for any of the following reasons:

- An adverse event too severe to allow continuation
- Gross patient non-compliance (e.g. if compliance of drug intake is less than 80% on two consecutive visits)
- A significant protocol violation as determined by the Study Committee
- Elevation of ALT or AST of more than 3 times the upper limit of normal
- Elevation of CPK more than 10 times the upper limit of normal, or presumed or assured diagnosis of a rhabdomyolysis
- Elevation of serum-creatinine more than 2 mg/dL
- Pregnancy or nursing occurring during the trial
- Intake of a HMG-CoA reductase inhibitor (other than the study medication) during the course of the study

If a patient is withdrawn from the study the patient should be invited to attend an Early Discontinuation Visit, the reasons for removal from the study and the date of last use of study medication should be recorded.

Patients discontinuing because of an adverse event must continue to maintain contact until the event resolves or is stable, and the information must be documented by the investigator.

Patients who did not receive any medication because of withdrawal prior to the administration of the first dose will not be assigned a patient number, and data obtained up to that point will not be entered in the study database.

Patients withdrawn from the study during the first nine months after the first intake of study drug will be replaced.

7 TREATMENTS TO BE ADMINISTERED

Atorvastatin (or matching placebo) will be supplied as 40 mg tablets for oral administration. The patients will take study medication in the evening on a daily base. The daily dose of atorvastatin or (matching number of Placebo tablets) will be 40 mg during the first four weeks of treatment and 80 mg from the fifth week till the end of the study. In case of side effects (e.g. myalgia) the dose may be reduced to 40 mg/day by the discretion of the investigator.

7.1 Identity of Investigational Product

To achieve blinding of the study medication to patients and investigators, atorvastatin and placebo will be indistinguishable from each other on the basis of all directly observable characteristics such as shape, size, appearance, weight, taste, odor, finish and dissolution characteristics.

7.2 Labeling and Packaging of the Investigational Product

Packaging, labeling and shipping of the investigational product will be performed by Profil GmbH in accordance with Profil's applicable standard operating procedures Study medication will be provided in containers which will be closed with a child-resistant closure. There will be a label bearing information that will meet the applicable regulatory requirements. The study medication will be supplied with a certificate of analysis.

7.3 Drug Accountability

It is the responsibility of each investigator to ensure that all study drug received at the site will be inventoried and accounted for throughout the study and the result recorded in the drug accountability form maintained in the investigator's study file. Patients must be instructed to return all original containers, whether empty or containing study drug. Study drug returned by patients will be stored and disposed of according to the manufacturer's instructions. Contents of the study drug containers must not be combined. The drug accountability will be verified by the site monitor during on-site monitoring visits. Study drug will be stored under appropriate environmental conditions.

The study drug will not be supplied to any person other than investigators, designated staff and the patients participating in the study. Study drug may not be relabeled or reassigned for use by other subjects except under special circumstances approved by the responsible Study Coordinator at Profil GmbH.

The investigators will retain and store all original containers returned by subjects, until these containers are inventoried by Profil. The investigators agree to return all

original containers at the end of the study, whether empty or containing study drug, to Profil as instructed by the site monitor. The investigators agree neither to dispense the study drug from, nor store it at, any site other than the study sites agreed upon with Profil.

Profil will ensure proper disposition of original containers whether empty or full with returned or unused study drug. Appropriate documentation will be maintained. Permission may be granted for local disposition, with supporting documentation.

7.4 Blinding

Blinded treatment will be used to reduce potential bias during data collection and evaluation of clinical endpoints.

The investigators will have code break envelops to be opened upon specific instructions by Profil's Study Coordinator or in case of life-threatening situation which is supposed to be related to the study drug or the study drug might interfere with the patient's further medical care. The study coordinator/monitors should be informed within 24 hours about the code break. Individual code breaks by an investigator will normally result in withdrawal of the subject from the trial. The date, time, and reason for the unblinding must be documented on the appropriate page of the CRF and in the source document.

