2.2 Administrative Structure

Principal Investigator: [name]. [name]

German Diabetes Clinic D-40225 Düsseldorf

Study Committee: [name]. [name]

[name]. [name]

[name]. [name]

German Diabetes Clinic D-40225 Düsseldorf

Coordinating Center Profil Institute for Metabolic Research GmbH

D-41460 Neuss

Safety Review Board: two independent outside expert and a representative of

Profil GmbH. All members of the Safety Review Board will be physicians who will otherwise not be involved in the conduction of the study. The members of the Safety Review Board will be appointed prior to study initiation.

This study is supported by an academic grant from Pfizer GmbH, D-76032 Karlsruhe

The German Diabetes Clinic will participate with approximately 25 to 35 patients.

Profil GmbH will serve as a coordinating center and will be responsible for

- study monitoring
- participation in site selection
- training and supporting the investigators and site staff in all study related procedures
- supplying sites with study medication and study materials
- labeling, packaging, storage, shipping and disposal of study medication
- randomization procedures

- design, distribution, review and archiving of CRF-documents
- participation in the external Safety Review Board
- data management
- quality assurance
- implementation of a service as a "Central Telephone Call-Center" for the study sites
- · collection of adverse events
- 24-hour-hotline for reporting of severe adverse events.

The Safety Review Board will consist of three physicians (two outside experts and a Profil representative). Informal safety analysis will be performed 6-monthly or more frequently, if required. The Safety Review Board will take part in an interim analysis after 40 percent of all participants will have completed twelve months of treatment. Randomization code will only be broken to investigators, if necessary for reasons of safety. Decisions will be taken on the discretion of the Safety Review Board and the Study Committee .Decisions will be protocolled. Any changes to the protocol as a result of the data review will be made as amendments to the protocol.

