9.4 Definition of Study Populations for Analysis

All patients who received at least one dose of study treatment will be included in the analysis of safety.

All patients who complete the study, will be included in the analysis of immune response and efficacy. The immune results of patients who drop out before completion of the study will be analyzed in a descriptive manner. If the study should be prematurely stopped after an interim analysis (see section 9.9), the study population for clinical efficacy will be defined as all patients who completed Visit 5 after 12 Months of treatment.

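### Withdrawal as the normal result of a code break (7.4), combined with completers-only efficacy (9.4), removes patients from the primary comparison for a reason that can depend on treatment

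*Protocol*

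**What the plan says.** Section 7.4 describes when the code may be opened: "The investigators will have code break envelops to be opened upon specific instructions by Profil's Study Coordinator or in case of life-threatening situation". The situation must be thought to be related to the study drug; possible interference of the drug with further medical care is also given as a ground. The consequence follows: "Individual code breaks by an investigator will normally result in withdrawal of the subject from the trial". The break must also be recorded: "The date, time, and reason for the unblinding must be documented on the appropriate page of the CRF and in the source document".

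Three other provisions decide what withdrawal means for the analysis:

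- Section 9.4, efficacy population: "All patients who complete the study, will be included in the analysis of immune response and efficacy".
- Section 6.5, replacement: "Patients withdrawn from the study during the first nine months after the first intake of study drug will be replaced".
- Section 5.3.7 and the flow chart in 5.2: the Early Discontinuation Visit has no mixed meal test and no C-peptide sample.

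The safety population in 9.4 is wider: "All patients who received at least one dose of study treatment will be included in the analysis of safety".

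Section 2.2, in the paragraph on the Safety Review Board, has its own sentence on the code: "Randomization code will only be broken to investigators, if necessary for reasons of safety".

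**The concern.** A code break happens after randomisation, and some code breaks are prompted by events that a physician suspects the study drug caused. If such events are more frequent or more severe in one arm, removal from the efficacy set will also differ between arms, and the patients who remain are no longer the groups that were randomised.

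Unblinding alone is a weak reason to stop collecting the primary endpoint. Once the patient is withdrawn, the 12- and 18-month mixed meal tests are not done. A statistical analysis plan could redefine the population, but it could not recover tests that were never performed. That makes this a matter for the protocol.

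**Working it through.** The protocol states no figure on this point, so the check is mainly a reading of the passages together.

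**What happens to a patient withdrawn after a code break, by timing**

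- *First nine months:* the patient is replaced (6.5). Neither the 12- nor the 18-month mixed meal test is done. The number of completers is restored, but by a different patient.
- *After nine months, before Visit 4:* no replacement and no mixed meal test after baseline.
- *Between Visit 4 and Visit 5:* a 12-month test exists, but the patient has not completed the study and so falls outside the 9.4 efficacy set. The separate 12-month definition in 9.4 applies only if the trial is stopped early after the interim analysis.

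In each case the patient stays in the safety analysis and leaves the efficacy analysis. The withdrawal sentence in 7.4 does not do this alone; it needs 9.4 and 5.3.7 as well.

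**Number of patients (assumption)**

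No code-break rate is given. Assume 1 to 5 patients in total:

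- 1/160 = 0.6%; 5/160 = 3.1%.
- If all fell in one arm of 80: 1/80 = 1.25%; 5/80 = 6.25%.

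**Possible shift in an arm mean (illustration)**

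If a fraction f of an arm is removed, and those removed would have differed on average by D from those retained, the retained mean differs from the full-arm mean by f × D. Take D as one standard deviation from section 9.1, 0.053 nmol/l (an assumption):

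- f = 1.25%: 0.0125 × 0.053 = 0.0007 nmol/l.
- f = 6.25%: 0.0625 × 0.053 = 0.0033 nmol/l.

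The difference targeted in 9.1 is 0.20 × 0.37 = 0.074 nmol/l, so these shifts are about 0.9% and 4.5% of it. They scale directly with f and D. Section 9.1 works in stimulated C-peptide concentration rather than area under the curve, so this shows order of magnitude only.

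**Power**

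Taking the 9.1 inputs at face value, with 80 per group:

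- Standard error = 0.053 × √(2/80) = 0.00838.
- z = 0.074 / 0.00838 = 8.83, against a two-sided 0.01 critical value of 2.58. Power exceeds 0.999.
- With 70 per group: standard error = 0.053 × √(2/70) = 0.00896 and z = 8.26. Power still exceeds 0.999.

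On the protocol's own inputs the losses do not threaten power. What remains is selection.

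**The case against.** The strongest objection is that the root problem is the completer population in 9.4, which affects every withdrawal, and that code breaks are a small part of it. A patient with a life-threatening event could often be discontinued anyway, because 6.5 allows this for an adverse event too severe to continue. The extra loss caused by the 7.4 sentence alone cannot be isolated from the document. This stands as a limit on size. It does not remove the point, because 7.4 makes withdrawal from the trial, not merely from study drug, the usual outcome, and 9.4 then excludes the patient.

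A second objection is that unblinded follow-up can be biased. This is partly right. Insulin dose, HbA1c, dose reduction and adverse event judgements are all in the investigator's hands. A reader might infer from the central C-peptide assay (8.16) that knowing the arm cannot affect the result. The protocol does not support that: the assay protects the measurement, not the management that precedes it. This argues for recording the break and running a sensitivity analysis, not for leaving the endpoint uncollected.

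Three further readings go beyond the text:

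- *That 7.4 lets the coordinating centre order a break for any reason, contradicting 2.2.* Section 7.4 states no criterion for the coordinator's instruction, which is silence rather than permission, and it requires the reason to be recorded. The 2.2 sentence sits in the Safety Review Board paragraph and may concern only what that review discloses. The coordinating centre also collects adverse events and runs the 24-hour hotline, so its instruction may be meant as a safety route. The sections can be read together, though the wording leaves this open.
- *That every code break removes the patient.* Section 7.4 says this is the normal result, which leaves discretion. It refers to breaks by an investigator, and whether one ordered by the coordinator counts is unclear.
- *That 6.5 conflicts with 7.4 because it does not list code breaks.* Section 6.5 lists permitted reasons, and 7.4 can add another.

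**Conclusion.** The point holds in limited form. Sections 7.4, 9.4 and 5.3.7 together take a patient withdrawn after a code break out of the primary comparison and stop collection of the endpoint, and 6.5 replaces the patient if this occurs in the first nine months. Because one trigger is suspected drug-related harm, the loss can depend on treatment; that it will differ by arm is plausible but not shown.

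The size is probably small: 0.6% to 3.1% of 160 patients if 1 to 5 code breaks are assumed, with no rate in the document to confirm it. Power is not the issue, and safety data are retained. The change is worth making because it is cheap and the missing tests cannot be recovered afterwards. The difference between 2.2 and 7.4 is a separate, smaller matter of wording to reconcile, not a demonstrated contradiction.

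**What to change.** - **7.4:** replace the withdrawal sentence with a statement that a code break is documented, does not by itself end trial follow-up, and that the patient is asked to keep the scheduled visits and mixed meal tests. The patient's right to withdraw is unchanged.
- **9.4:** include these patients in the efficacy analysis in the arm to which they were randomised, with a sensitivity analysis excluding data collected after unblinding. Without this change, the edit to 7.4 would not by itself secure their place in the comparison.
- **2.2 and 7.4:** reconcile the two descriptions of when the code may be broken, including the criterion for a coordinator's instruction and whether such a break counts as one by an investigator. Which rule applies is for the sponsor and its safety physicians to settle.

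Whether study drug continues after a code break is a separate clinical decision and is not addressed here.

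The cost is a few sentences in an amendment, and visits and tests that are already in the schedule. Finances are in a separate contract (13.6), so the budget effect cannot be checked. The statistical price is a small amount of unblinded data, which matters more for insulin dose, HbA1c and adverse event judgement than for centrally assayed C-peptide.
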